### **13.8 Overall Survival**

Overall survival is defined as the time from the start of treatment to death due to any cause.

## 13.9 Clinical Benefit Rate

The CBR is defined as the proportion of patients who achieved overall tumor response (CR or PR) or SD for at least 24 weeks. Stable disease is measured from enrollment until the criteria for disease progression or response are met, per RECIST v1.1

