#### *1.4.6.1 Neratinib Single-agent Activity in Patients with HER2+ Breast Cancer*

Early clinical data have demonstrated the activity of neratinib in patients who have already failed other small molecule or antibody-based HER2 targeted therapies. In the single-agent, first-in-human phase I study of neratinib in solid tumor, a 32% objective response rate (ORR) was observed among patients with trastuzumab refractory HER2+ disease [5]. Specifically, 8 of 25 patients had partial response (PR). Among the responders, two PRs occurred at neratinib doses of 120 or 180 mg per day, which was below the recommended monotherapy dose. All of these responders had prior trastuzumab therapy, notably six patients had received at least four trastuzumab-based therapies. Additionally, all had received prior anthracycline and gemcitabine, and the majority (7/8) had received prior taxane therapy. Six patients had also received prior capecitabine therapy.

An open-label, multicenter, Phase 2 study evaluated the efficacy and safety of neratinib 240 mg daily, in patients with and without prior trastuzumab treatment, who had advanced HER2+ breast cancer. The primary end point, the 16-week PFS rates, was 59% and 78% in prior trastuzumab-treated patients and trastuzumab-naïve cohorts, respectively [4]. The ORR was 24% and 56%, respectively, and the median PFS times were 22.3 and 39.6 weeks, respectively. Mean steady-state trough concentrations for the 240 mg daily dose exceeded concentrations needed to inhibit autophosphorylation of HER2 in preclinical models [18].

The most common adverse events (AE) were diarrhea, nausea, vomiting, and fatigue. Diarrhea was the most frequent Grade 3 to 4 AE, occurring in 30% of patients with prior trastuzumab treatment and in 13% of trastuzumab-naïve patients, which resulted in dose reductions of 29% and 4% of patients, respectively. However, treatment discontinuation (TD) occurred in only one patient due to diarrhea (Grade 2). No neratinib-related Grade 3 or 4 cardiotoxicity was reported. Additional information regarding previous clinical studies of neratinib for treatment of HER2+ breast cancer is provided in the current Investigator's Brochure.

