### 6.1 Screening Procedures

#### 6.1.1 General Guidelines

Eligible patients will be entered on study at the participating sites and centrally at the City of Hope Comprehensive Cancer Center. See **Appendix C** for Multicenter Guidelines. An Eligibility Screening Worksheet is attached as **Appendix G**.

Following registration, patients should begin protocol treatment after receiving the oral medication and after being told to do so by the study team. Issues that would cause treatment delays should be discussed with the Principal Investigator. If a patient does not receive protocol therapy following registration, the patient's registration on the study may be canceled. The Data Coordinating Center should be notified of cancellations as soon as possible.

Diagnostic or laboratory studies performed exclusively to determine eligibility for this trial will be done only after obtaining written informed consent. Studies or procedures that were performed within 2 weeks for clinical indications (not exclusively to determine study eligibility) may be used for baseline values, even if the studies were done before informed consent was obtained.

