## **8.0 Dose Delays/Modifications for Adverse Events**

---

Patients will be treated per protocol or until disease progression or withdrawal from treatment due to unacceptable adverse events or treatment consent withdrawal. At each study assessment, subjects are to be evaluated for evidence of drug-related adverse events.

In all cases where the subject is withdrawn due to unusual or unusually severe adverse event considered related to neratinib, the Investigator must report the withdrawal as a Serious Adverse Event.

Treatment may be delayed for up to 4 weeks, to allow for resolution of toxicity except in the event of those toxicities described below in which cases treatment must be discontinued permanently (see **Table 7**).

Recommended dose reductions for the -1 and -2 dose levels of Neratinib are listed as following:

Dose level	Neratinib
Starting dose	240mg
-1	160mg
-2	120mg

If a dose of neratinib is held, study procedures for that cycle will proceed on schedule as planned, without any delay. This also applies to tumor assessments, which should continue to be done every 12 weeks, starting from the first dose of neratinib until the first planned tumor assessment at 12 weeks ( $\pm 1$  wk), and then after every subsequent 12 weeks ( $\pm 1$  week) of treatment regardless of any changes in dose or occurrence of AEs. Missed dose(s) of neratinib (i.e., any

dose that is not administered within the protocol-defined administration window) will not be made up. The dose adjustment guidelines represent the minimum set of measures that investigators must follow. However, additional measures may be taken as necessary, for certain patients per the Investigator's medical judgment. All dose modifications/adjustments should be documented in the patient's source file.

Once neratinib dose has been reduced for a patient, all subsequent cycles must be administered at that dose, unless further dose reduction is required. Dose re-escalation is not permitted.

If a patient developed AE requiring dose reduction while on neratinib dose level of 120mg, neratinib will be discontinued.

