### **13.1 Response Criteria**

For the purposes of this study, patients should be reevaluated for response every 12 weeks. Response and progression will be evaluated in this study using the new updated international criteria proposed by the Response Evaluation Criteria in Solid Tumors (RECIST) Committee version 1.1. Per the RECIST criteria, as disease response is not the primary endpoint of this trial, confirmatory scans following documentation of progression or response will not be required. Rather, progression/response will be determined based on results of the single scan.

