### **13.6 Duration of Response**

Duration of overall response: The duration of overall response is measured from the time measurement criteria are met for CR or PR (whichever is first recorded) until the first date that recurrent or progressive disease is objectively documented (taking as reference for progressive disease the smallest measurements recorded since the treatment started).

Duration of stable disease: Stable disease is measured from the start of the treatment until the criteria for progression are met, taking as reference the smallest measurements recorded since the treatment started.

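### Section 13.9 stops the stable-disease clock at the scan that shows progression, so a patient who progresses on the week-24 scan can count as 24 weeks of stable disease and raise the clinical benefit rate

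*Combined protocol and SAP*

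**What the plan says.** Section 13.9 defines the CBR as the "proportion of patients who achieved overall tumor response (CR or PR) or SD for at least 24 weeks". It then fixes the clock: "Stable disease is measured from enrollment until the criteria for disease progression or response are met".

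Section 13.6 has a different start but the same stop at progression: "Stable disease is measured from the start of the treatment until the criteria for progression are met". PFS (13.7) and OS (13.8) also start at treatment, so 13.9 alone starts at enrollment.

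On the calendar, 13.1 says "patients should be reevaluated for response every 12 weeks". Section 8.0 sets the origin of the schedule, "starting from the first dose of neratinib until the first planned tumor assessment at 12 weeks", and then every 12 weeks (±1 week). Section 13.1 requires no confirmation: "progression/response will be determined based on results of the single scan".

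On the order of events, 6.1.1 says: "Following registration, patients should begin protocol treatment after receiving the oral medication". No maximum interval from registration to first dose is given.

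The Statistical Considerations part of the synopsis and section 15.3 give clinical benefit as CR+PR+SD with no minimum duration.

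**The concern.** The 24-week threshold coincides with a scheduled scan, and the clock stops on the date of the scan that shows PD. A patient can therefore meet the threshold by means of the scan that documents failure. No section requires the week-24 scan to be free of progression.

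CBR is a stated secondary objective, to be reported with exact 95% limits. Those limits describe sampling error. They do not reflect a classification rule that adds week-24 progressors to the numerator and removes no one. When enrollment and first dose are close together, a few days of scan timing also decide whether two patients with the same disease course are classified alike.

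**Working it through.** The documents give no expected CBR, so there is no figure to reproduce. The check has two parts: date arithmetic, then an illustration of size.

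**1. Dates.** Cycles are 28 days. Three cycles after Day 1 is Cycle 4 Day 1 = Day 85, where the schedule places the first on-treatment scan. Three more give Cycle 7 Day 1 = Day 169, which is 168 days (24 weeks) after first dose. For PD first seen on this scan, the 13.9 duration is

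duration = 168 + offset + lag (days),

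where offset runs from −7 to +7 (the ±1 week window) and lag is the time from enrollment to first dose, at least 0 because treatment follows registration (enrollment is taken as registration). The patient counts if duration ≥ 168, that is, if offset ≥ −lag.

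| Lag (assumed) | Qualifying days in the 15-day window |
|---|---|
| 0 days | 8/15 (53%) |
| 3 days | 11/15 (73%) |
| 7 days or more | 15/15 (100%) |

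At lag 0, PD seen on Day 162 does not count and PD seen on Day 169 does. Using the 13.6 start (first dose) is the same as setting lag to 0: on-time and late PD scans still qualify. The stop rule is therefore the main driver. The enrollment start adds the early in-window scans.

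**2. Share of patients exposed.** Section 1.4.6.1 reports that "the median PFS times were 22.3 and 39.6 weeks" in the prior-trastuzumab and trastuzumab-naïve cohorts. Eligibility centers on failed anti-HER2 therapy, so the first value is used, with an exponential curve (an assumption):

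- λ = ln 2 / 22.3 = 0.0311 per week
- S(12) = exp(−12λ) = 0.689; S(24) = exp(−24λ) = 0.474
- S(12) − S(24) = 0.214, about 8.6 of 40

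As a check on the curve, S(16) = 0.608 against the 59% reported for that cohort. Fitting to the 59% instead gives 0.673 − 0.453 = 0.220.

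**3. Inflation at lag 0, scans spread evenly over the window.**

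- If none of the week 12–24 events is in a responder: 0.214 × 8/15 = 0.114. The CBR goes from 47.4% to 58.9% (about 19.0 to 23.5 of 40).
- If the cited 24% ORR is spread proportionally over patients progression-free at week 12, then 0.24/0.689 = 0.348 of them are responders and count anyway. The exposed share is 0.214 × (1 − 0.348) = 0.140, and 0.140 × 8/15 = 0.074. The CBR goes from 54.9% to 62.3% (about 22.0 to 24.9 of 40).

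The range is thus roughly 7 to 11 points, or about 3.0 to 4.6 of 40 patients.

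**The case against.** Stopping a duration at documented progression is this protocol's general convention: 13.6 does it for SD and 13.7 for PFS. That is true, and as a descriptive duration it is ordinary. The difficulty arises only when the duration is dichotomized at a value equal to a scan date, which 13.9 does.

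The size is soft, and this objection stands. S(12) − S(24) treats every event in the interval as first found at the week-24 scan. PFS events include deaths, and 7.7.2.1 allows symptom-driven scans; events documented before 168 days from enrollment are not misclassified. Off-study imaging is done only if clinically indicated, so some patients will have no week-24 scan. The synopsis places scans at the end of every three cycles; a scan on Day 168 is 167 days after first dose and, at lag 0, does not qualify. The denominator may be below 40, because 13.1 limits response evaluability to measurable disease while 5.1 admits non-measurable disease.

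Three stronger readings are tempting and are not supported.

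- A reader might infer that the enrollment start is the cause and that aligning 13.9 with 13.6 cures it. It does not: an on-time week-24 PD scan still reaches 168 days.
- A reader might quote 14 to 21 points (0.140 to 0.214 with every in-window scan qualifying). That needs a lag of at least 7 days, which the documents do not give, and the top also needs no responders among these patients.
- A reader might say that a week-23 PD scan never counts. That holds only for lags under 7 days.

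Finally, if the analysis follows 15.3 literally, the 24-week clock never operates and editing 13.9 alone changes nothing. This also stands, so the sections must be reconciled together.

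**Conclusion.** The point holds. As written, 13.9 lets a patient with SD at week 12 and PD on an on-time or late week-24 scan count as clinical benefit, and nothing elsewhere prevents it. This follows from the dates alone and needs no model. Measured against a rule requiring freedom from progression at the week-24 scan, the mechanism can only raise the CBR.

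The size of roughly 7 to 11 points is illustrative. It rests on exponential PFS with the cited median, no enrollment-to-dose lag, scans even over ±1 week, and all week 12–24 events first being found at the week-24 scan. A lag would increase it; the features listed under the objection would reduce it. For scale, 15.1 gives about 0.16 as the widest 95% half-width at n = 40. The shift is smaller than that, but it goes one way and the interval does not reflect it.

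The consequence is limited to a descriptive secondary rate with no hypothesis or decision attached. The correction is worth making because it is cheap and the direction is known.

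**What to change.** In 13.9, define clinical benefit as best response of CR or PR, or SD with no progression documented on or before the week-24 (±1 week) scan, shown by that scan or a later one being progression-free. State that patients with no such scan do not qualify through SD, and that a clear scan anywhere in the ±1 week window is accepted as meeting 24 weeks, since a clear week-23 scan is otherwise ambiguous. Start the clock at first dose, as in 13.6. Make the synopsis and 15.3 refer to this definition in place of CR+PR+SD without a duration.

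The cost is a text edit in three places and a somewhat lower reported CBR. No extra scans or data are needed, and the primary endpoint, sample size and stopping rule do not change.

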## 14.0 Data Reporting/Protocol Deviations

---

### 14.1 Data Reporting

#### 14.1.1 Confidentiality and Storage of Records

Electronic Data Collection will be used for this protocol. The data will be stored in encrypted, password protected, secure computers that meet all HIPAA requirements. When results of this study are reported in medical journals or at meetings, identification of those taking part will not be disclosed. Medical records of subjects will be securely maintained in the strictest confidence, according to current legal requirements. They will be made available for review, as required by the FDA, HHS, or other authorized users such as the NCI, under the guidelines established by the Federal Privacy Act and rules for the protection of human subjects.

#### 14.1.2 Subject Consent Form

At the time of registration, the original signed and dated Informed Consent form, HIPAA research authorization form, and the California Experimental Subject's Bill of Rights (for the medical record) and three copies (for the subject, the research record, and the Coordinating Center) must be available. All Institutional, NCI, Federal, and State of California requirements will be fulfilled.

#### 14.1.3 Data Collection Forms and Submission Schedule

All data will be collected using electronic data collection, stored as indicated in Section 12.1.1, and submitted according to the timelines indicated in **Table 16**.

**Table 16: Data Submission Schedule**

Form	Submission Timeline
Eligibility Checklist	Complete prior to registration
On Study Forms	Within 14 calendar days of registration
Baseline Assessment Forms	Within 14 calendar days of registration
Treatment Forms	Within 10 calendar days of treatment administration
Adverse Event Report Forms	For Cycle 1 only, within 7 calendar days of AE assessment/notification; for all other cycles, within 10 calendar days of AE assessment/notification
Response Assessment Forms	Within 10 calendar days of the response assessment
Other Assessment Forms (as applicable)	Within 10 calendar days of the assessment

Off Treatment/Off Study Forms	Within 10 calendar days of completing treatment or being taken off study for any reason
Follow up/Survival Forms	Within 14 calendar days of the protocol defined follow up visit date or call

#### *14.1.3.1 Eligibility Checklist*

The Eligibility Checklist must be completed by a protocol nurse or clinical research associate and signed by an authorized investigator prior to registering the subject. See Section 4.3 for the registration procedure.

### **14.2 Protocol Deviations**

#### 14.2.1 Deviation Policy

This protocol will be conducted in accordance with COH's "Clinical Research Protocol Deviation Policy" located at

<http://www.coh.org/dsmc/Documents/Institutional%20Deviation%20Policy.pdf>.

Deviations from the written protocol that could increase patient risk or alter protocol integrity require prior IRB approval of a single subject exception (SSE) request. In addition, if contractually obligated, the sponsor must also approve the deviation. IRB pre-approved SSE protocol modifications are considered an amendment to the protocol and not a deviation. The submission of a deviation report is not required.

Brief interruptions and delays may occasionally be required due to travel delays, airport closure, inclement weather, family responsibilities, security alerts, government holidays, etc. This can also extend to complications of disease or unrelated medical illnesses not related to disease progression. The PI has the discretion to deviate from the protocol when necessary so long as such deviation does not threaten patient safety or protocol scientific integrity. Examples include, but are not limited to: a) dose adjustments based on excessive patient weight; b) alteration in treatment schedule due to non-availability of the research participant for treatment; c) laboratory test results which are slightly outside the protocol requirements but at levels that do not affect participant safety. These instances are considered to be deviations from the protocol. A deviation report will be submitted to the DSMC/IRB within five days.

#### 14.2.2 Reporting of Deviations

All deviations will be reported to the COH DSMC within five days. The DSMC will forward to report to the IRB following review.

#### 14.2.3 Resolving Disputes

The COH Investigational Drug Service (IDS) cannot release a research agent that would cause a protocol deviation without approval by the PI. Whenever the protocol is ambiguous on a key point, the IDS should rely on the PI to clarify the issue.

In situations where there is misperception or dispute regarding a protocol deviation among the persons involved in implementing the protocol, it is the responsibility of the PI to resolve the dispute and the PI may consult with the DSMC chair (or designee) to arrive at resolution.

## **15.0 Statistical Considerations**

---

The study will be an open label, single arm, phase II safety and tolerability study of neratinib (240 mg orally daily) in patients age 60 or older with HER2 positive breast cancer. As diarrhea has been seen with neratinib, we have established additional guidelines and criteria which will be used to flag an unexpected number of patients that experience grade 3 diarrhea within the 2 cycles on neratinib treatment in the presence of aggressive mandatory anti-diarrhea management which will lead to a careful data review. There will also be one interim analysis of the toxicity profile after 20 subjects have been on drug for one cycle.

### **15.1 Sample Size and Accrual Rate**

Given a sample size of 40 subjects the widest half-width of the 95% confidence limits for the rate of grade 2 or higher toxicities will be less than or equal to 0.16. For example if we saw a toxicity rate of 0.2 (8 subjects/40) the 95% lower and upper confidence limits would be .09 and .36, respectively. With a sample size of 40, we would expect to see toxicity that has a true rate of occurrence of 0.05 in 87% of trials. We expect an accrual rate of 3 subjects every 2 months, for a total accrual rate of 18 subjects per year. With this rate, the full complement of 40 subjects will be accrued over a 30 month period. The median number of cycles for this patient population is approximately 9, so we would expect to complete this study in 42 to 48 months.

### **15.2 Interim Analyses and Stopping rules**

#### **15.2.1 Interim Analyses**

After 20 patients have completed one full cycle of therapy, the study team will review the data, determine the rate of grade 2 and above toxicities attributed (level possibly and above) to neratinib, and assess the toxicity profile in general and specifically look at all grades of GI toxicities. We will also estimate the rates of dose reduction, holds, and hospitalization related to the neratinib. Within this interim analysis we will include a specific review the data from the participants over 75 years of age.

#### **15.2.2 Stopping Rules (see Table 17)**

As diarrhea has been seen with neratinib, we have established additional guidelines and criteria which will be used to flag an unexpected number of patients that experience grade 3 diarrhea within the 2 cycles on neratinib treatment in the presence of aggressive mandatory anti-diarrhea management.

The risk set to be used in the safety monitoring decision (to trigger a review of the protocol) will include all patients that have received the neratinib in the presence of aggressive mandatory anti-diarrhea management.

Every time a patient experience  $\geq$  grade 3 diarrhea within the first 2 cycles on treatment in the presence of aggressive mandatory anti-diarrhea management we will look at the column for the total number of patients that have experienced this toxicity (X), and compare the total number of patients, N, who are in the risk set to Nx. If the total number of patients, N, is greater than Nx, the number given in the bottom row of the table below, then accrual will continue. If N is less than or equal to Nx, then the monitoring boundary will have been crossed and a careful review of the trial data will be mandated.

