**Table 5: Loperamide Dosing**

Day	Loperamide Dose
1	4mg at time of first dose of neratinib, then 12mg in 3 divided dose of 4mg tid
2-14	Daily dose of 12 mg in 3 divided doses of 4 mg tid
15-28	Daily dose of 8 mg in 2 divided doses of 4 mg bid
29+	Daily dose as needed (not to exceed 16 mg per day)

Patients must use a diary to record intake of loperamide. Loperamide pill counts will be conducted during the first 2 cycles (56 days) of therapy.

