### **Definitions**

Evaluable for toxicity: All patients will be evaluable for toxicity from the time of their first treatment with Neratinib.

Evaluable for objective response: Only those patients who have measurable disease present at baseline, have received at least one cycle of therapy, and have had their disease re-evaluated will be considered evaluable for response. These patients will have their response classified according to the definitions stated below. (Note: Patients who exhibit objective disease progression prior to the end of cycle 1 will also be considered evaluable.)

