**Table 17: Criteria for Suspending Accrual to Evaluate Safety**

X: # pts who experience $\geq$ grade 3 diarrhea within the first 2 cycles on neratinib treatment in the presence of aggressive mandatory anti-diarrhea management.	4	5	6	7	8	9	10	11	12
Nx: safety boundary crossed if # patients in risk set (N) is less than or equal to Nx (if $N \leq Nx$ )	$\leq 6$	$\leq 11$	$\leq 16$	$\leq 20$	$\leq 25$	$\leq 29$	$\leq 34$	$\leq 38$	$\leq 40$

These rules were selected to ensure a low probability that the safety boundary would be crossed, indicating excessive  $\geq$ grade 3 diarrhea, if the true chance of  $\geq$ grade 3 diarrhea were less than 15% and a high probability that the boundary would be crossed if the true chance of  $\geq$ grade 3 diarrhea reached 30%. Criteria for flagging an excessive number of patients that have toxicity are based on the sequential probability ratio test with  $a=0.10$ ,  $b=0.10$ ,  $po=0.15$  and  $pa=0.30$ . The table below summarizes these probabilities. The values in **Table 18** below are based on 10,000 simulations.

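### The diarrhea boundary counts patients in N from first dose although the event window is 56 days; this modestly lowers and delays the flag at a true 30% rate

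*Combined protocol and SAP*

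**What the plan says.** Section 15.2.2 counts in X the patients with diarrhea at or above "grade 3 diarrhea within the first 2 cycles on treatment in the presence of aggressive mandatory anti-diarrhea management". The text under Table 5 gives the length of that window: "Loperamide pill counts will be conducted during the first 2 cycles (56 days) of therapy". At each new event the team is to "compare the total number of patients, N, who are in the risk set to Nx", and Table 17 states the rule as "safety boundary crossed if # patients in risk set (N) is less than or equal to Nx". The risk set "will include all patients that have received the neratinib in the presence of aggressive mandatory anti-diarrhea management". The definitions in section 13.1 take the same line: "All patients will be evaluable for toxicity from the time of their first treatment with Neratinib". No section delays entry to N, weights partial follow-up or pauses accrual while outcomes are pending.

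The text under Table 17 bases the boundary on a sequential probability ratio test with a=0.10, b=0.10, p0=0.15 and pa=0.30. It adds: "The values in Table 18 below are based on 10,000 simulations". No accrual or onset assumption is given for those simulations. On accrual, section 15.1 says: "We expect an accrual rate of 3 subjects every 2 months". Section 7.6.1.1 describes diarrhea onset as typically falling in the first few weeks of treatment.

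**The concern.** X and N do not refer to the same patients. A patient can enter X at any time over 56 days but enters N on the first day of dosing. Event-free patients still inside the window count as if they were known non-events, so N is too large for the X it is compared with.

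A simple case shows the mechanism. Suppose four patients have known outcomes and all four had the event, and three more have just started. Then N=7, which exceeds 6, and accrual continues. On the four known outcomes N=4 and the boundary is crossed. Because the boundary is checked only when an event occurs, a crossing missed this way is not revisited until the next event.

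At stake is the diarrhea boundary that governs suspension of accrual. If it flags later, more patients are dosed before the review. Table 18 gives only 0.71 at a true 30% rate, so there is little sensitivity to spare.

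**Working it through.** **Inputs from the plan.** Nx = 6, 11, 16, 20, 25, 29, 34, 38, 40 for X = 4 to 12 (Table 17); a, b, p0 and pa as above; maximum 40 patients; 1.5 patients per month (section 15.1); 56-day window (Table 5 text). Table 18: <0.001, 0.07, 0.71 and >.99 at true rates of 5%, 15%, 30% and 50%.

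**Assumptions, because the plan is silent.** Poisson entry. Onset uniform over days 0-14, 0-28 or 0-56, or exponential with mean 3-20 days; reporting lag 0-7 days. All events at day 56 is an extreme case.

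**Step 1: the boundary.** Solve ln((1-b)/a) = X·ln(pa/p0) + (N-X)·ln((1-pa)/(1-p0)) for N. With ln 9 = 2.197, ln 2 = 0.693 and ln(0.70/0.85) = -0.194, N = X + (0.693X - 2.197)/0.194. For X = 4 to 12 this gives 6.96, 11.53, 16.10, 20.67, 25.24, 29.81, 34.38, 38.95 and 43.52. Rounded down and capped at 40, these are the Nx row exactly.

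**Step 2: Table 18.** An exact patient-by-patient recursion over Table 17, with each outcome known before the next patient enters, gives 0.0003, 0.061, 0.714 and 0.999. This fits Table 18 closely at 30% and less tightly at 15% (0.061 against 0.07).

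**Step 3: patients pending.** 1.5 × 56/30.44 = 2.8 patients start in any 56 days. In simulation about 2 event-free patients are still in their window at each check during accrual.

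**Step 4: the rule under staggered entry, 1.5 per month.** Here the alternative N counts a patient once the event has occurred or 56 days have passed. Each pair is as written / alternative.

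| Onset | Crossing at true 30% | Crossing at true 15% | Mean patients dosed at flag (30%) |
|---|---|---|---|
| Days 0-14 | 0.70 / 0.77 | 0.057 / 0.093 | 19.3 / 17.9 |
| Days 0-28 | 0.69 / 0.77 | 0.054 / 0.088 | 19.8 / 18.5 |
| Days 0-56 | 0.68 / 0.75 | 0.047 / 0.076 | 20.9 / 19.4 |
| All at day 56 (extreme) | 0.66 / 0.70 | 0.034 / 0.064 | 23.5 / 21.5 |

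With instantly known outcomes the mean dosed at the flag is 18.8. Over the wider set of onset and lag assumptions, leaving out the day-56 extreme, the written rule crosses in 0.67-0.71 at 30%. Where both rules flag at 30%, the written one is on average about 1.6 months and 2.3 patients later.

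**Step 5: how much of the gain is dilution.** The event-or-56-days N admits events at once but non-events only after 56 days, which pushes the observed rate up. Weighting each event-free patient by the elapsed share of the assumed onset period removes dilution without that asymmetry. It gives 0.71 / 0.70 / 0.70 at 30% for the three uniform patterns, against 0.70 / 0.69 / 0.68 as written: 0-2 points recovered.

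**Step 6: the two candidate definitions of N, Nx unchanged.**
- Event or 56 days: about 0.74-0.78 at 30% and 0.08-0.10 at 15% at planned accrual. At an assumed 3 per month, 0.09-0.14 at 15%.
- Weighted by the fraction of 56 days followed: about 0.69-0.73 at 30% and 0.05-0.07 at 15% at planned accrual. At 3 per month, at or below 0.08 at 15%.

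At 3 per month the written rule gives 0.65-0.70 at 30% over the three uniform patterns.

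**The case against.** The strongest reply is that the effect is nearly nil under the plan's own conditions. Accrual is slow and onset is described as early. With exponential onset of mean 5 days the written rule crosses in 0.71 of trials at 30%, equal to Table 18; with onset over days 0-14 or 0-28 the loss is 1-2 points. This stands, and it limits the size of the point.

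Crossing the boundary also triggers a data review rather than termination, and other oversight does not depend on N: calls in the first three days (7.6.1.2), early nurse visits (7.7.3.1), cycle 1 adverse event forms within 7 days (Table 16) and the interim review after 20 patients complete a cycle (15.2.1). This also stands. It lowers the stakes but does not align N with the event window.

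The worked case under the concern is improbable: at a 30% rate, four events in the first four patients has probability 0.3^4 = 0.008. It shows the mechanism, not a typical loss.

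A reader might infer that Table 18 must have been simulated without staggered entry, since the instant-outcome model reproduces it. The documents do not support that. The simulation is not described, the written rule with staggered entry can also reach 0.71 at 30%, and the instant-outcome figure at 15% is not a tight match.

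**Conclusion.** The mismatch is real and nothing elsewhere in the plan corrects it. At planned accrual and a true 30% rate, the rule as written crosses in about 0.67-0.71 of trials, 0-4 points below Table 18 (0-2 points with early onset), and flags somewhat later. The direction does not depend on the onset pattern, but the size does. Onset distributions, Poisson entry and reporting lag are assumptions, and patients stopping before day 56 were not modelled because the plan gives no rate. Faster accrual or later onset enlarges the loss.

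A reader might infer that dilution costs about 7 points, the gap between the written rule and the event-or-56-days version. Step 5 shows otherwise: most of that gap comes from counting events at once and non-events late. Nor does it follow that the new N can simply be used with the present Nx row, because at 3 per month crossing at 15% can exceed a=0.10. This is a modest improvement to the monitoring rule, not a major defect.

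**What to change.** In section 15.2.2, define N in one of two ways:
- patients who have had the event or completed 56 days (counted from first dose, so that patients who stop early without the event still enter N); or
- all dosed patients, with each event-free patient still in the window weighted by the fraction of 56 days followed.

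Rerun Table 18 with staggered entry at 1.5 per month and a stated onset assumption, and restate its row. Keep the Nx row only if crossing at a true 15% rate stays within a=0.10. The event-or-56-days version might need an adjusted Nx if accrual runs faster than planned; the weighted version stays at or below 0.08 even at 3 per month, but gains less at 30%.

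The cost is a revised definition and one rerun of a simulation. The gain is about 0.5-1.5 fewer patients dosed on average at the flag when the true rate is 30%. The downside is a somewhat higher chance of an unnecessary data review at a true 15% rate: from about 0.05-0.06 to 0.08-0.10 with the first definition, or to 0.05-0.07 with the second.
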